5.0 TREATMENT PLAN

Four weeks on therapy is considered one cycle of therapy. INCB018424 and lenalidamide will be given orally in an outpatient setting. INCB018424 will be given continuously daily in 28-day cycles, and lenalidamide will be given on days 1-21 of 28 day cycles. Dosage for cycles can be reduced, increased or delayed based assessment of efficacy and on adverse events, if any occur, as described below. Delays of a maximum of 8 weeks are allowed from scheduled next cycle.

Subjects will be asked to maintain a diary to record drug administration. Subjects will be asked to bring any unused study drug to the research center at their next visit. Research personnel will count and record the number of used and unused study drug capsules/tablets (both ruxolitinib and lenalidomide) at each visit and reconcile with the subject diary. The study coordinator will question the patient regarding adherence to the dosing regimen, record the number of capsules/tablets and strengths returned in the carton, the date returned and determine treatment compliance before dispensing new medication to the study patient. Compliance below 80% will require counseling of the patient by study site personnel.

The planned dose and schedule of investigation of INCB018424 is 15 mg orally twice daily (BID), continuously in 28-day cycles. Lenalidomide will be taken orally 5 mg/day in the morning each day on days 1-21, followed by 7 days of no therapy of each 28-day cycle; medication will be mailed to participants, per the RevAssist® Program.

Twenty eight days is considered one cycle of therapy. Attempts will be made to provide an adequate treatment period of at least 6 months unless significant toxicity observed, to account for delayed time to response observed with biologic agents. Responders will continue therapy for 6 years unless progression of disease or toxicity warranting discontinuation of therapy is observed.

Prednisone will be added for patients who have not responded after 3 cycles of therapy. It will be dosed orally at the dose of 30 mg/day during cycle 4, 15 mg/day during cycle 5, and 15 mg every other day during cycle 6, and then it will be discontinued.

All patients will be registered in the Clinical Oncology Research system(CORE) at MD Anderson Cancer Center after the informed consent is signed.

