- A letter to the local physician outlining the patient's participation in a clinical trial will request local physician agreement to supervise the patient's care (Appendix L)
- Protocol required evaluations outside MDACC will be documented by telephone, fax or e-mail. Fax and/or e-mail will be dated and signed by the MDACC physician, indicating that they have reviewed it.
- Changes in drug dose and/or schedule must be discussed with and approved by the MDACC physician investigator, or their representative prior to initiation, and will be documented in the patient record.
- A copy of the informed consent, protocol abstract, treatment schema and evaluation during treatment will be provided to the local physician.
- Documentation to be provided by the local physician will include drug administration records, progress notes, reports of protocol required laboratory and diagnostic studies and documentation of any hospitalizations.
- The home physician will be requested to report to the MDACC physician investigator all life threatening events within 24 hours of documented occurrence.
- Patients will return to MDACC every 2 weeks during Cycles 1 and 2, monthly for 2 cycles, then every 3 to 6 months as long as on the study for evaluation.

The patient will be contacted by the PI and his staff 30 days and 60 days after discontinuation of protocol +/-7 days to assess for AE's, unless the patient receives further cytotoxic chemotherapy treatment.

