5.7 Criteria for Removal from the Study

Treatment with study drugs is to be discontinued when any of the following occurs:

- Lack of therapeutic effect (any effort should be made to provide therapy to the patient in a safe way for at least 3-6 cycles for proper assessment of potential efficacy)
- Adverse event(s) that, in the judgment of the Investigator, may cause severe or permanent harm or which rule out continuation of study drug.
- Withdrawal of consent
- Lost to follow up
- Death
- Suspected pregnancy

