8.0 STATISTICAL CONSIDERATIONS

All subjects meeting the eligibility criteria that have signed a consent form and have begun treatment will be evaluable for response. This is a two stage, phase II trial designed to assess the effect of therapy in subjects with Primary, Post Polycythemia Vera, or Post Essential Thrombocythemia Myelofibrosis (PMF, post-PV MF, or post-ET MF). Secondary objective is to determine the safety of therapy in this population.

The primary objective of this study is to assess efficacy in terms of the objective response rate (complete and partial response, and clinical improvement by IWG-MRT) in patients with MF. The Min-Max two-stage design proposed by Simon will be implemented. Sample size and decision criteria are chosen to reduce the expected accrual if the treatment is ineffective in regard to response relative to having no interim stopping rule. The target response rate is 50%. A response rate of 35% or less will be considered unacceptable and treatment with the therapy will be discontinued. Given the response rates stated above, if the probability of inappropriately accepting a poor therapy is 10% ($\alpha=0.1$), a total sample size of 49 patients will result in 80% power ($\beta=0.2$).

In the first stage of the design, a total of 31 patients will be enrolled and the study will be put on hold to assess response. If 10 or fewer patients respond to the combination therapy, after being treated for 6 months or discontinued due to excessive toxicity or lack of efficacy, then the study will be terminated and the therapy will be declared ineffective. Those patients who stopped receiving one of the two study drugs due to safety reasons will be counted as failures in the efficacy analysis. However, if 11 or more patients respond, up to an additional 18 patients will be enrolled to complete the study.

After a total of 49 patients have been enrolled into the study, if 21 or fewer patients respond to the therapy, the therapy will be declared ineffective. However, if greater than 21 patients respond to the therapy, the therapy will be considered efficacious. The probability of early termination due to unacceptable response rate is 46% under the null hypothesis.

Data from all subjects who receive any study drug will be included in the safety analyses. Subjects who entered the study and did not take any of the study drug and had this confirmed, will not be evaluated for safety.

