The severity of the toxicities will be graded according to the NCI CTCAE v4.0 whenever possible. We will follow standard reporting guidelines for adverse events (Appendix C; Leukemia-specific Adverse Event Recording and Reporting Guidelines).

Descriptive statistics will be utilized to assess time to response and response duration.

Duration of response: duration of response is defined as the date at which the subject's objective status is first noted to be a CR, PR or CI to the date progression (no longer meeting criteria for either CR, PR or CI) is documented (if one has occurred). Patients who continue to respond as of the data cut-off date will be censored as of the date of their last assessment documenting continued response.

Time to response: The time to response is defined as the time from study registration to the first date at which the subject's objective status was classified as a response (CR, PR or CI). In subjects who do not achieve a response, time to response will be censored at the subject's last evaluation date. The distribution for each of these event-time variables (duration of response and time to response) will be estimated by Kaplan-Meier curves.

Anemia: Descriptive statistics will be used to explore improvements in anemia and transfusion dependence. The following outcomes will be summarized: mean changes in hemoglobin at monthly intervals. The proportion of transfusion independent patients not requiring transfusions on study who experience an increase of 2 g/dL in their hemoglobin relative to baseline, the proportion of transfusion dependent patients (defined as requiring a transfusion of 2 units PRBCs monthly for 3 months (12 weeks) prior to starting the trial) who become transfusion independent (not requiring a transfusion of PRBCs over a period of 3 months (12 weeks) while on study), the proportion of transfusion dependent patients who become transfusion independent and have a 1 g/dL increase in hemoglobin relative to baseline, and the proportion of transfusion independent patients requiring a transfusion while on study.

JAK2V617F Allele burden: Change in JAK2V617 allele burden from baseline to each visit where it is measured.

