APPENDIX I: SCHEDULE OF ASSESSMENTS

Procedure	Screening Period ≤14 days from Day 1 (first day of study drug administration)	Cycle 1 ⁹ and 2				Cycle 3 ⁹ Every 28 days	After Cycle 3 or at discontinuation ⁹ Every 3 to 6 Cycles (84 to 168 days)
		Day 1 ⁵	Day 8	Day 15	Day 22		
Informed Consent signing	X						
Medical History (including prior MF-directed therapies)	X						
Physical examination ¹	X	X		X		X	X
Vital Signs and Weight, Height ¹¹	X	X		X		X	X
Transfusion History ²	X ²					X	X
MFSAF and MDASI questionnaires		X				X	X
Pregnancy test (for FCBP only) ³	X	X	X	X	X	X	X
CBC and differential ⁶	X	X	X	X	X	X ⁶	X ⁶
Serum Chemistry ⁴	X	X	X	X	X	X ⁶	X ⁶
12-Lead ECG and urinalysis	X						
Bone Marrow Aspirate and Biopsy ⁷	X						X ⁸
Correlative studies for PK: Peripheral blood sample x3	-	X ¹⁰					
Assess and Record adverse events	X	X		X		X	X
Record concomitant therapies/procedures	X	X		-		X	X
Response Assessment					X	X	X

¹ Includes measurement of spleen and liver.

² Subjects must have 3 months documented transfusion history prior to Day 1.

³ Pregnancy test, urine or blood, with a sensitivity of at least 50 mIU/mL, within 10 – 14 days prior to and again within 24 hours of starting lenalidomide; then every week x 4, then monthly for all FCBP with regular menstrual cycles, or every 2 weeks if irregular cycles.

⁴ sodium, potassium, chloride, carbon dioxide, blood urea nitrogen, creatinine, total bilirubin, alanine aminotransferase, and glucose. Uric Acid, PT/PTT and INR need be done only pre-therapy.

⁵ If not done within 3 days of Day 1.

⁶ CBC with differential and serum chemistries will be done weekly for 2 cycles, then every 2 weeks while on therapy. Those responding patients continuing therapy past 6 cycles and on a stable dose level without interruption or delay for 4 cycles may have blood tests done monthly.

⁷ Bone Marrow Aspirate and Biopsy (can be done within 3 months) includes standard cytogenetic analysis and JAK2 mutation testing (quantitative PCR for allele burden). Cytogenetic test and JAK2 mutation test do not need to be repeated during the study in patients with known normal chromosomes or without mutation. BM collected after Cycle 3,6,9,12 and then as determined appropriate by the investigator.

⁸ May be omitted if so decided by the treating physician. Should be done to confirm complete response and when clinically indicated.

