- ⁹. All scheduled visits will have a +/- 7 days window unless otherwise stated. In between required MD Anderson visits, mandatory visits may be done at the local referring doctor's office at minimum every 28 days (+/- 7 days);, this will also include phone contact by the study staff. The discontinuation visit will be considered as such on the date the patient is taken off the protocol. The patient will be contacted by the PI 30 days and 60 days after discontinuation of protocol +/-7 days to assess for AE's.
- ¹⁰. on day 1 of cycle 2 for pharmacokinetics (PK) at approximately 0.5-1 hour, 2-4 hours, and 4-8 hours post Ruxolitinib dose (3 time points).
- ¹¹. Height at screening only

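### Time to response is estimated by Kaplan-Meier with patients who die or stop treatment censored, so the curve can rise above the proportion who actually respond

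*Combined protocol and SAP*

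**What the plan says.** Section 1.0 lists time to response as an exploratory objective. Section 8.0 measures it from registration to the first CR, PR or CI and calls the analysis descriptive. For everyone else the rule is "In subjects who do not achieve a response, time to response will be censored at" the last evaluation date, and the two event-time variables ("duration of response and time to response) will be estimated by Kaplan-Meier curves"). Neither death nor stopping treatment is treated differently, and no section names a competing-risk method.

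The plan expects patients to leave without a response. Section 5.7 lists reasons to stop that include death, adverse events and "Lack of therapeutic effect (any effort should be made to provide therapy" for 3 to 6 cycles first). The stage 1 rule in section 8.0 counts response "after being treated for 6 months or discontinued due to excessive toxicity or lack of efficacy". Section 5.0 adds an intention on timing: "Attempts will be made to provide an adequate treatment period of at least 6 months unless significant toxicity observed".

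Appendix I has a response assessment in the column headed "After Cycle 3 or at discontinuation", and its notes state that "The discontinuation visit will be considered as such on the date the patient is taken off the protocol". For the period after that, section 5.6 says "The patient will be contacted by the PI and his staff 30 days and 60 days after discontinuation of protocol", and the stated purpose of these contacts is adverse events. No later response assessment is scheduled.

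**The concern.** A non-responder who dies or leaves treatment is censored at about the time of exit and cannot be recorded as a responder later. Kaplan-Meier handles a censored patient as someone who would have gone on to respond at the rate of those still under assessment. That is hard to defend for a patient removed because the drugs were not working, and it has no meaning for a patient who has died.

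At stake is a descriptive curve that can level off above the trial's own response rate, so that one report carries two figures for the same patients. The contrast could be awkward. A count of 21 of 49 is the largest that section 8.0 still calls ineffective, yet under one of the assumed cases below the curve for that count reaches 50%, the target rate.

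**Working it through.** **The plan's own figures.** The documents give no figure for time to response. The primary design does reproduce. With 10/31 and 21/49 as the stopping limits, exact binomial calculation gives alpha 0.097 (limit 0.10), power 0.801 (stated 80%) and early termination under the null of 0.455 (stated 46%). None of these uses the time-to-response curve.

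**Inputs.** N = 49 and the limit of 21 responders come from section 8.0. The number and timing of exits, and the split into earlier and later responses, are assumptions. Section 2.3 supports some responses after week 24: with lenalidomide plus prednisone, a different combination, the median time to response was 12 weeks and the range 2 to 32.

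**Formula.** Suppose *a* patients respond by some time, *x* non-responders then leave, and *b* more respond later with no further exit before the last response. Then

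- one minus Kaplan-Meier = 1 − [(N − a)/N] × [(N − a − x − b)/(N − a − x)]
- proportion responding = (a + b)/N
- excess = b·x / [N(N − a − x)]

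The excess is positive when both *x* and *b* are above zero, and zero when either is zero. Whether the exit falls at a scheduled visit does not enter the formula; only its order relative to later responses does. The same pattern held in random data sets. One minus Kaplan-Meier was above the observed proportion in all 46,909 that had a censored non-responder before the last response, and equal to it in all 2,044 that did not.

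**Exits just after week 24** (a = 18, b = 3): 1 − (31/49) × (28 − x)/(31 − x)

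**Exits at week 12** (a = 11, b = 10): 1 − (38/49) × (28 − x)/(38 − x)

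| Non-responders leaving, of 28 | Responding, 21/49 | Curve, exits just after week 24 | Curve, exits at week 12 |
|---|---|---|---|
| 0 | 42.9% | 42.9% | 42.9% |
| 5 | 42.9% | 44.0% | 45.9% |
| 10 | 42.9% | 45.8% | 50.1% |
| 14 | 42.9% | 47.9% | 54.8% |

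For example, with x = 10 at week 12 the excess is 10 × 10 / (49 × 28) = 0.073, and 0.429 + 0.073 = 0.501 after rounding. A single exit just after week 24 adds only 3 × 1 / (49 × 30) = 0.002.

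The week 24 case fits the plan better. Week 12 is the end of cycle 3, the lower end of the range in section 5.7 for lack of effect and well short of the six months in section 5.0. Exits for toxicity could still come that early.

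**The case against.** The strongest reply is that Kaplan-Meier with exits censored can be read as time to response had nobody left, and section 8.0 never says that the curve is to be read as the proportion responding. On that view the choice of cumulative incidence is partly preference. This stands only in part: the plan does not declare that hypothetical quantity, and it would require that those who leave have the same prospects as those who stay.

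Two further replies stand. The endpoint is exploratory and no decision uses it. Section 2.2 also describes spleen responses to ruxolitinib as rapid, and early responses leave few to come after an exit. Against that, section 5.0 adds prednisone from cycle 4 for patients who have not responded, so later responses remain plausible.

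Some stronger readings are not supported:

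- **That the efficacy conclusion is inflated.** The primary analysis counts responders against fixed limits and does not use the curve.
- **That the long gaps between later assessments (every 3 to 6 cycles in section 5.6) make the excess much larger.** That needs a schedule with no reading near week 24, whereas the stage 1 rule in section 8.0 judges response after six months of treatment. It also needs exit rates that the documents do not give.
- **That exits recorded at a scheduled visit do no harm.** Week 12 is a scheduled assessment, and the week 12 case shows up to 12 points of excess.
- **That all censoring here is wrong.** Censoring a patient still on treatment without response at data cut-off is proper.

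**Conclusion.** The point holds for this exploratory curve. As written, one minus Kaplan-Meier exceeds the cumulative proportion responding whenever a non-responder dies or permanently stops treatment before the last recorded response, and equals it if none does. The direction is certain; the size is not. Under the assumed exits of 5 to 14 of 28 non-responders, the excess is about 1 to 5 points for exits just after week 24 and about 3 to 12 points for exits at week 12. It would be smaller with fewer exits or earlier responses. It is worth correcting because the correction is cheap, not because any decision of the trial depends on it.

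**What to change.** In section 8.0, replace the Kaplan-Meier estimate of time to response with a cumulative incidence estimate:

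- **Competing events:** death, and permanent discontinuation of all study treatment, before response.
- **Censoring:** only at data cut-off, loss to follow-up or withdrawal of consent.
- **Responder definition:** the one used in the primary analysis, which counts patients who stop one of the two drugs for safety as failures. Such a patient is not an event on the curve. He or she is a competing event from the date that drug is stopped or, if a response had already been recorded, is shown as a non-responder in line with the primary analysis.
- **Agreement with the response rate:** state that the curve ends at the observed response rate only if no patient is lost or withdraws before the last response, and give the number of such patients. Section 8.0 keeps them evaluable for the response rate, so some difference can remain.
- **Reporting:** give the median time to response among responders beside the response rate.

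The cost is a change of wording and a standard routine. The notes to Appendix I define the off-protocol date, and section 5.1 already requires the reason for discontinuing study drug to be documented. The sample size, visit schedule and decision rule do not change. The downside is that the plotted probability of response may be lower than with Kaplan-Meier.

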1.0 HYPOTHESIS AND OBJECTIVES

Hypothesis

Ruxolitinib (also known as INCB018424), a JAK1/2 inhibitor, and lenalidomide (immunomodulatory inhibitory drug; IMiD) are effective and tolerable treatments for patients with myelofibrosis (MF). Combination of these agents in patients with MF can improve the overall clinical response to therapy without causing excessive toxicity.

Objectives

Primary:

- to determine the efficacy of the combination of INCB018424 with lenalidomide in patients with MF, in achieving objective improvements in disease status

Secondary:

- to determine the safety of the combination in patients with MF

Exploratory:

- to explore time to response and duration of response
- to explore the effect of the combination on anemia and transfusion dependence in patients with MF
- to explore changes in JAK2V617F allele burden

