To investigate the safety and efficacy of the combination of lenalidomide and prednisone in patients with MF, 40 patients were treated. Therapy consisted of lenalidomide 10 mg/d (5 mg/d if baseline platelet count < 100 x 10⁹/L) on days 1 through 21 of a 28-day cycle for six cycles, in combination with prednisone 30 mg/d orally during cycle 1, 15 mg/d during cycle 2, and 15 mg/d every other day during cycle 3. Lenalidomide therapy was continued indefinitely in patients exhibiting clinical benefit. The median follow-up was 22 months (range, 6 to 27). Responses were recorded in 12 patients (30%) and are ongoing in 10 (25%). The median time to response was 12 weeks (range, 2 to 32). According to the International Working Group for Myelofibrosis Research and Treatment consensus criteria, three patients (7.5%) had partial response and nine patients (22.5%) had clinical improvement durable for a median of 18 months (range, 3.5 to 24+). Overall response rates were 30% for anemia and 42% for splenomegaly. Moreover, 10 of 11 assessable responders who started therapy with reticulin fibrosis grade 4 experienced reductions to at least a score of 2. All eight JAK2^{V617F}-positive responders experienced a reduction of the baseline mutant allele burden, which was greater than 50% in four, including one of whom the mutation became undetectable. Grade 3 to 4 hematologic adverse events included neutropenia (58%), anemia (42%), and thrombocytopenia (13%). The combination of lenalidomide and prednisone induced durable clinical, molecular, and pathologic responses in MF.

Most frequently reported adverse events reported during clinical studies with lenalidomide in oncologic and non-oncologic indications, regardless of presumed relationship to study medication include: anemia, neutropenia, thrombocytopenia and pancytopenia, abdominal pain, nausea, vomiting and diarrhea, dehydration, rash, itching, infections, sepsis, pneumonia, UTI, Upper respiratory infection, cellulitis, atrial fibrillation, congestive heart failure, myocardial infarction, chest pain, weakness, hypotension, hypercalcemia, hyperglycemia, back pain, bone pain, generalized pain, dizziness, mental status changes, syncope, renal failure, dyspnea, pleural effusion,

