5.3 Concomitant Therapy

All supportive measures consistent with optimal subject care will be given throughout the study. Concomitant medications will be captured in the CRF beginning at screening. Packed red blood cell or platelet transfusions are allowed when necessary. Growth factor use (including erythropoietin) is not allowed with the exception of the use of filgrastim (G-CSF) or pegfilgrastim, which is permitted ONLY when used to treat febrile neutropenia or in patients who have prolonged (one week or more) grade 3-4 neutropenia, after approval from Principal Investigator. Concomitant use of cytotoxic chemotherapeutic agents (e.g. hydroxyurea), or other experimental drug or therapy for myelofibrosis while the subject is on study is prohibited. Concurrent use of strong inducers or strong inhibitors of CYP3A4 (strong inducers are rifampin and St. John's Wort; strong inhibitors are HIV-antivirals, clarithromycin, itraconazole, ketoconazole, nefazodone, and telithromycin) is prohibited.

Lenalidomide increases the risk of thrombotic events in patients who are at high risk or with a history of thrombosis, in particular when combined with other drugs known to cause thrombosis. When lenalidomide is combined with other agents such as steroids (e.g. dexamethasone, prednisone), anthracyclines (Doxil, adriamycin) and erythropoietin the risk of thrombosis is increased. Consideration should be given to the use of aspirin (81 or 100 mg) as prophylaxis as deemed appropriate (through commercial supply, not provided by the Incyte or Celgene companies). When the platelet count falls below $35 \times 10^9/L$, aspirin prophylaxis should be discontinued until the platelet count is $> 35 \times 10^9/L$ and stable (not less than prior measurement) or increasing on two consecutive measurements at least 4 days apart.

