6.0 CRITERIA FOR RESPONSE

Best overall response will be categorized according to the International Working Group Criteria:

Complete remission (CR): Requires all of the following in the absence of both transfusion and growth factor support;

- Complete resolution of disease-related symptoms and signs including palpable hepatosplenomegaly.
- Peripheral blood count remission defined as hemoglobin > 11 g/dL, platelet count $\geq 100 \times 10^9/L$, and absolute neutrophil count $\geq 1.0 \times 10^9/L$.
- Normal leukocyte differential including disappearance of nucleated red blood cells and immature myeloid cells in the peripheral smear, in the absence of splenectomy.*
- Bone marrow histological remission defined as the presence of age-adjusted normocellularity, < 5% myeloblasts, and an osteomyelofibrosis grade of ≤ 1 .**

Partial remission (PR): Requires all of the above criteria for CR except the requirement for bone marrow histological remission. However, a repeat bone marrow biopsy is required in the assessment of PR and may or may not show favorable changes that do not however fulfill criteria for CR.

Clinical improvement (CI): Requires one of the following in the absence of both disease progression (as outlined below) and CR/PR assignment (*CI response is validated only if it lasts for ≥ 8 weeks*).

- A ≥ 2 g/dL increase in hemoglobin level or becoming transfusion independent (applicable only for patients with baseline hemoglobin level of < 10 g/dL).[§]
- Either a $\geq 50\%$ reduction in palpable splenomegaly of a spleen that is ≥ 10 cm at baseline or a spleen that is palpable at > 5 cm at baseline becomes not palpable.^{§§}
- A $\geq 100\%$ increase in platelet count and an absolute platelet count of $\geq 50,000 \times 10^9/L$. (applicable only for patients with baseline platelet count of < $50 \times 10^9/L$).
- A $\geq 100\%$ increase in ANC and an ANC of $\geq 0.5 \times 10^9/L$ (applicable only for patients with baseline absolute neutrophil count of < $1 \times 10^9/L$).

Progressive disease: Requires one of the following:[¶]

- Progressive splenomegaly that is defined by the appearance of a previously absent splenomegaly that is palpable at > 5 cm below the left costal margin or a $\geq 100\%$ increase in palpable distance for baseline splenomegaly of 5-10 cm or a $\geq 50\%$ increase in palpable distance for baseline splenomegaly of > 10 cm.
- Leukemic transformation confirmed by a bone marrow blast count of $\geq 20\%$.

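### The hemoglobin-rise proportion in Section 8.0 drops patients transfused on study from its denominator instead of counting them as non-responders

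*Combined protocol and SAP*

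**What the plan says.** Section 1.0 places this question among the exploratory objectives: "to explore the effect of the combination on anemia and transfusion dependence in patients with MF". Under Anemia, Section 8.0 states "Descriptive statistics will be used to explore improvements in anemia and transfusion dependence" and lists the outcomes. The item at issue is "The proportion of transfusion independent patients not requiring transfusions on study who experience an increase of 2 g/dL in their hemoglobin relative to baseline". The last item in the list is "the proportion of transfusion independent patients requiring a transfusion while on study". The list also has monthly mean hemoglobin changes and two proportions for patients who were transfusion dependent at baseline. For those patients, becoming independent means 12 weeks on study without a red-cell transfusion.

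The hemoglobin item has no time window, and no rule says how a patient transfused on study is to be counted. Section 5.3 makes such transfusions possible: "Packed red blood cell or platelet transfusions are allowed when necessary". Treatment can be long: "Responders will continue therapy for 6 years unless progression of disease or toxicity warranting discontinuation of therapy is observed" (Section 5.0).

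Elsewhere the groups are fixed at or before the start of treatment. For the primary response, Section 8.0 makes all eligible, consented patients who began treatment evaluable. In Section 6.0 the hemoglobin criterion for clinical improvement is limited by a baseline value only, "applicable only for patients with baseline hemoglobin level of < 10 g/dL", and clinical improvement must last at least 8 weeks.

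**The concern.** The hemoglobin item follows the pattern of a group followed by a who-clause that names the event. The on-study transfusion condition stands before the who-clause, in the group. The denominator is therefore selected on a post-baseline event, and one that is itself bad news for an anemia endpoint.

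This has a perverse consequence. With the number of untransfused responders held fixed, the more patients the regimen sends to transfusion, the better the rate looks. Because no window limits the on-study period and responders may be treated for years, the denominator can also shrink as follow-up lengthens.

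The excluded group need not be small. Section 2.3 reports grade 3 to 4 anemia in 42% of patients in the cited study of lenalidomide plus prednisone. That is neither a transfusion rate nor this regimen, so it shows only that the issue is realistic.

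What is at stake is how this single-arm trial's effect on anemia is described in patients who were transfusion independent at entry.

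**Working it through.** **1. The plan's own figures.** Section 8.0 gives no expected value for this proportion, so there is nothing to reproduce directly. The only design figures are those of the two-stage rule (stop at 10 or fewer of 31; ineffective at 21 or fewer of 49; response rates 35% and 50%). Exact binomial calculation gives a type I error of 0.097, power of 0.801 and a probability of early termination under the null of 0.455. These agree with the stated 10%, 80% and 46%. The hemoglobin proportion is not an input to any of them.

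**2. Notation.**
- n: patients transfusion independent at baseline
- T: those of the n who are transfused on study, with t = T/n
- R: untransfused patients with a rise of at least 2 g/dL
- S: transfused patients who would still count as responders

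**3. Rates when transfused patients are non-responders (S = 0).**
- As worded: R/(n - T)
- All baseline transfusion-independent patients: R/n
- Ratio: n/(n - T) = 1/(1 - t)

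**4. Size.** The documents give neither n nor t. Assume, for illustration only, n = 30 and R = 6, so the all-patient rate is 6/30 = 20.0%.

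| T | t | Rate as worded | Ratio |
|---|---|---|---|
| 3 | 10% | 6/27 = 22.2% | 1.11 |
| 6 | 20% | 6/24 = 25.0% | 1.25 |
| 9 | 30% | 6/21 = 28.6% | 1.43 |
| 12 | 40% | 6/18 = 33.3% | 1.67 |
| 15 | 50% | 6/15 = 40.0% | 2.00 |

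The number of responders is the same in every row. The ratio depends on t alone, so the choice of n and R does not affect it.

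**5. Can a reader undo it?** The last item in the list is t. Multiplying, R/(n - T) x (n - T)/n = R/n. In the T = 9 row, 28.6% x 0.70 = 20.0%. This works if both proportions use the same patients and the same period.

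**6. How far the result depends on the non-responder rule.** If some transfused patients also count as responders, the all-patient rate is (R + S)/n. The rate as worded is higher only while S/T is below R/(n - T). With n = 30, T = 9 and R = 6, the rate as worded is 28.6%. The all-patient rate is (6 + 2)/30 = 26.7% for S = 2 and (6 + 3)/30 = 30.0% for S = 3. The direction therefore reverses if transfused patients respond at least about as often as untransfused ones.

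**The case against.** The strongest reply is that the phrase may be meant as part of the event: untransfused and up by 2 g/dL, out of all transfusion-independent patients. The last item in the list, "the proportion of transfusion independent patients requiring a transfusion while on study", has a similar form, and there the transfusion is clearly the event. On that reading the bias disappears. The parallel is weak, however, because the last item has no who-clause, while the hemoglobin item has one and puts the transfusion condition ahead of it. If the numerator reading was intended, the same one-sentence change settles it.

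A second reply is that transfusion raises hemoglobin, so transfused patients cannot be judged. That is a reason to keep a transfusion-driven rise out of the numerator, not to remove the patient from the denominator.

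Third, the summary is exploratory and descriptive, with no test or target. The transfused proportion is reported beside it, and monthly mean hemoglobin changes are listed without a transfusion restriction. All of this stands and limits the importance of the point.

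Four stronger readings are tempting, and the documents do not support them.
- A reader might infer that everyone whose anemia worsened is excluded. Only transfused patients are; those whose hemoglobin fell without transfusion stay in and lower the rate.
- A reader might infer that the rate is certainly inflated. That holds only if transfused patients are non-responders, and Section 8.0 does not state such a rule.
- A reader might add that omitting the limit of hemoglobin below 10 g/dL inflates the rate further. Nothing in the documents gives that direction. Including non-anemic patients makes the figure harder to set beside Section 6.0, but could as easily lower it.
- A reader might conclude that any transfusion on study should void a response. Without a window, a durable responder transfused once, years later, would become a failure. That would sit badly with the 8-week rule in Section 6.0.

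**Conclusion.** The point holds as a defect of one exploratory summary. On the plain reading, the denominator is selected on a post-baseline event and patients transfused on study drop out. If they are non-responders, the reported rate exceeds the rate in all baseline transfusion-independent patients by 1/(1 - t): 1.11 at 10% transfused, 1.43 at 30% and 2.00 at 50%. The formula is exact under that assumption. The value of t is not in the documents, so the actual size is unknown. If some transfused patients would qualify as responders, the excess is smaller and can reverse.

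It would be wrong to infer that the trial's efficacy conclusion is at risk. The primary response uses all eligible treated patients, its hemoglobin criterion is restricted by baseline only, and the 10/31 and 21/49 rules do not use this proportion. The change is still worth making: it removes an avoidable bias and settles an ambiguous sentence.

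**What to change.** Replace the item in Section 8.0 with a definition along these lines.

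- **Denominator:** all treated patients who are transfusion independent at baseline. Say what that means, since Section 8.0 defines dependence (2 units monthly for 3 months) but not independence at entry.
- **Responder:** a hemoglobin rise of at least 2 g/dL from baseline with no red-cell transfusion during a stated window around that rise. The 8 weeks that Section 6.0 requires for clinical improvement is one choice already in the protocol.
- **Non-responder:** every other patient in the denominator, including those transfused without meeting the responder definition.
- **Optional:** the same rate in the subgroup with baseline hemoglobin below 10 g/dL, to line up with Section 6.0.

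Keep the separate transfused proportion, and show counts with both proportions so that the denominators are visible.

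The cost is a small edit to Section 8.0. No new data are needed, because blood counts and transfusion history are already collected (Sections 5.5 and 5.6, Appendix I). The reported rate will probably be somewhat less favorable than under the present wording.
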